18.3 Statistical Approach to Secondary and Exploratory Endpoints

A pre-planned analysis of the secondary endpoints will be performed testing the non-inferiority, followed by superiority, of the Experimental Arm compared to the Control Arm conditioned by success in testing of the primary efficacy endpoint. The multiplicity and Type 1 Error within the secondary endpoints' family will be controlled using the fixed sequence approach and alpha value of 0.05. SAP provides details on the analysis of the secondary endpoints including non-inferiority margins, where applicable.

Statistical approaches for exploratory endpoints are described in SAP.

18.4 Sample Size Determination

Under the assumption that the proportion of completely healed ulcers by day 84 is 0.8 (80%), the sample size of 206 subjects and minimum of 206 wounds randomized 1:1 to Experimental and Control arms will have 85% power to reject the null hypothesis.

Sample size assumptions concerning the proportion variance and average number of wounds per subject will be verified during the study in a blinded fashion. Such verification does not inflate alpha-value.

18.5 Multiplicity

Testing of secondary endpoints will be performed in a gateway fashion and fixed sequence. No adjustment for the multiplicity is required. Details of the fixed sequence will be presented in SAP.

18.6 Randomisation

Subjects will be randomised on a 1:1 basis to either the AQUAUCEL® Ag+ Extra™ or Cutimed® Sorbact® dressing at the subject level. All wounds for the same subject will be treated using the randomised dressing. The randomization sequence will be stratified by study centre. Other details concerning the randomization are described in the Randomisation Plan.

18.7 Statistical Populations

All subjects that are randomized are considered participants.

Safety Population includes all subjects that are randomized to and receive one of the study treatments.

Full Analysis Data Set. This will be constructed following the Intent-to-Treat (ITT) principle and will include all subjects that are randomized, receive one of the study treatments, and have at least one follow-up visit after the baseline (Visit 1).

Per Protocol Population (PP) This will all subjects that are randomized, receive one of the study treatments, do not discontinue the trial prior to 4-week follow-up visit except for the reason that all study ulcers have closed and have no major protocol deviations that would impact integrity of the statistical analysis of primary endpoint.

Completed Cases (CC) Population is a subset of Full Analysis Data Set Population and includes all subjects who have the final study visit (Day 84) or have exited the study earlier due to all study wounds have healed.

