8.1 Point of Enrolment

Subjects are considered enrolled in this study at the time the Informed Consent process has been completed. In the event of subject withdrawal or discontinuation prior to study completion, study subjects will not be replaced.

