8.2 Point of Exit

Study subjects may exit the study for a variety of reasons. The Investigator shall record the reason for study exit in the applicable Study Completion CRF. These reasons include, but are not limited to:

- Study completion.
- Withdrawal by the Subject.
- Withdrawal by the Investigator.
- Lost to follow-up.
- Death.
- Study Termination.

Data collected until the last known contact of study subject may be used in the analysis of study data. For study subjects lost to follow-up, the Investigator shall make three (3) documented attempts before confirming the subject is lost to follow-up. If the study subject withdraws from the study for any reason and there is an ongoing safety event, additional safety event information may need to be collected by the Investigator and shared with the Sponsor.

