8.3 Completed Subject

Subject has completed the study if the subject has completed the final study visit (84 days follow-up visit) or earlier if all study wounds have healed prior to 84-day follow-up visit. If subject has multiple wounds, the subject exits the study when the last study wound heals or when subject attends the final study visit, whichever occurs first. Study completion can occur between the scheduled study visits.

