18.2 Statistical Approach for the Primary Endpoint

The study hypothesis is that the Experimental Treatment with AQUACEL® Ag+ Extra™ will have similar effectiveness to the Control Treatment with Cutimed® Sorbact® in proportion of wounds that have completely healed by 84 days. The statistical hypothesis is that Experimental Treatment with AQUACEL® Ag+ Extra™ will be non-inferior to Control Treatment with Cutimed® Sorbact® in proportion of wounds that have completely healed by 84 days.

The statistical null and alternative hypotheses are as follows:

$$\begin{aligned} H_0: \pi_{Exp} - \pi_{Con} &\leq \delta \\ H_A: \pi_{Exp} - \pi_{Con} &> \delta \end{aligned}$$

where π_{Exp} and π_{con} represent the true proportion of target wounds that have healed by 84 days in patients treated with AQUACEL® Ag+ Extra™ and Cutimed® Sorbact®, respectively, and δ is the non-inferiority margin. The non-inferiority margin (δ) is set to -15%.

The statistical definition of success is the rejection of H_0 . The null hypothesis (H_0) will be tested by constructing a two-sided 90% confidence interval for the difference in the proportions of ulcers that have completely healed between the Experimental Arm and the Control Arm. If the lower boundary of the interval does not include δ , then the null hypothesis will be rejected. If non-inferiority of AQUACEL® Ag+ Extra™ to the Cutimed® Sorbact is demonstrated, its superiority will be tested.

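### Does the Completed Cases set, which keeps early healers and drops subjects who leave unhealed, put the non-inferiority result at risk?

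*Combined protocol and SAP*

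**What the plan says.** Section 18.2 tests closure by Day 84 against a margin of -15 percentage points. The null hypothesis "will be tested by constructing a two-sided 90% confidence interval for the difference in the proportions of ulcers that have completely healed". The section names no analysis set and does not say how each arm's proportion is to be estimated when a wound has no Day 84 outcome.

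Section 18.7 defines the sets:

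- **Full Analysis**: built on the intent-to-treat principle. It takes randomised, treated subjects with at least one post-baseline visit.
- **Per Protocol**: subjects without major deviations who "do not discontinue the trial prior to 4-week follow-up visit except for the reason that all study ulcers have closed".
- **Completed Cases**: a subset of Full Analysis that "includes all subjects who have the final study visit (Day 84) or have exited the study earlier due to all study wounds have healed".

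Section 8.3 counts a subject as complete at the Day 84 visit, or "earlier if all study wounds have healed prior to 84-day follow-up visit". Section 8.1 says "study subjects will not be replaced". Section 8.2 says "Data collected until the last known contact of study subject may be used in the analysis of study data", which permits the use of partial data but does not say how to score them. The opening of Section 18 presents the section as key elements only and leaves the details to the SAP.

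**The concern.** Once all of a subject's wounds have healed, participation ends, so that subject can no longer be lost. Only subjects with an open wound can be. Completed Cases removes those who leave before Day 84 and keeps everyone who healed early. The healing proportion is then too high even if leaving has nothing to do with prognosis; it would not be too high only if leavers were going to heal better than those retained. Per Protocol shares this asymmetry up to Week 4.

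The bias is largest in the arm that loses more subjects, and an open-label trial can lose subjects unequally. If the experimental arm lost more, a dressing truly 15 points worse could pass too often. Because Section 18.2 names neither the deciding set nor a rule for leavers, the supplied text does not expressly prevent an analyst from resting the conclusion on Completed Cases.

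**Working it through.** **Inputs from the protocol.** One-sided alpha 0.05, through the two-sided 90% interval (18.1, 18.2); margin -0.15 (18.2); healing 0.80, 206 subjects randomised 1:1, so 103 per arm (18.4). No drop-out rate is given.

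**The plan's own figure.** With 0.80 in both arms, SE = sqrt(2 × 0.8 × 0.2 / 103) = 0.0557. Power = Φ(0.15/0.0557 - 1.645) = 0.852. This agrees with Section 18.4, where the sample "will have 85% power to reject the null hypothesis". It reproduces with one wound per subject and no loss.

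**Assumed loss model.** One wound per subject; six 14-day intervals; healing chance per interval h = 1 - (1 - p)^(1/6), which is 0.2353 for p = 0.80 and 0.1605 for p = 0.65. After each visit from Day 14 to Day 70 a share d of unhealed subjects leaves, unrelated to later healing.

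- Completed Cases proportion = observed healed / (observed healed + unhealed at Day 84), with n = 103 × (1 - lost).
- Leavers counted as not healed: observed healed over all 103.
- Kaplan-Meier: leavers censored, Greenwood variance.
- Chance of declaring non-inferiority = Φ((difference + 0.15)/SE - 1.645).

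**One line in full: truth 65% v 80%, leaving 6% v 2% per visit.**

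- Experimental: healed 0.5774, unhealed at Day 84 0.2569, lost 0.166. Completed Cases = 0.5774/0.8343 = 0.692, n = 85.9.
- Control: healed 0.7726, unhealed 0.1808, lost 0.047. Completed Cases = 0.7726/0.9534 = 0.810, n = 98.2.
- Difference -0.118, SE 0.0636. Φ(0.0317/0.0636 - 1.645) = 0.126.

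**Chance of declaring non-inferiority at the true limit (65% v 80%; nominal 5%)**

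| Leaving per visit, experimental v control | Lost by Day 84 | Completed Cases difference | Completed Cases | Leavers not healed | Kaplan-Meier |
|---|---|---|---|---|---|
| 2% v 2% | 5.9% v 4.7% | -14.7 | 5.6% | 5.3% | 5.0% |
| 6% v 6% | 16.6% v 13.2% | -13.9 | 7.1% | 6.0% | 5.0% |
| 3% v 2% | 8.7% v 4.7% | -14.0 | 7.0% | 3.5% | 5.0% |
| 6% v 2% after Days 14 and 28, then 2% in both | 11.6% v 4.7% | -14.0 | 6.9% | 1.7% | 5.0% |
| 6% v 2% throughout | 16.6% v 4.7% | -11.8 | 12.6% | 0.9% | 5.0% |
| 2% v 6% throughout | 5.9% v 13.2% | -16.7 | 2.7% | about 20% | 5.0% |

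Simulating the 6% v 2% line gave 13.1%, 0.9% and 5.2%. With an assumed 30% of subjects having two wounds (latent correlation 0.3), Completed Cases fell to 11.2%.

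**If leavers would heal worse.** The 5.0% in the Kaplan-Meier column follows from the assumption that leaving is unrelated to healing. At 6% v 2%, for Completed Cases / leavers not healed / Kaplan-Meier:

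- leavers would heal at half the rate: 21% / 2% / 9%
- leavers would never heal: 37% / 5% / 20%

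A second check takes equal shares in both arms, leavers who would never heal, and s as the share of Day 84 non-healers who leave. The Completed Cases rate is p/(p + (1 - p)(1 - s)). With s = 0.3 this is 0.65/0.895 = 0.726 against 0.80/0.94 = 0.851, a difference of -12.5 points. Simulated false non-inferiority is 11.6%, against 5.1% with leavers counted as not healed. With s = 0.2 it is 8.6%.

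**The case for a change.** The strongest case for a change is that the same data could pass or fail depending on a choice made later. With equal dressings (80% v 80%) and leaving of 6% v 2%, the chance of success is 92% on Completed Cases, 50% with leavers counted as not healed and 81% by Kaplan-Meier. Reversed to 2% v 6%, the figures are 75%, 95% and 81%. Naming the set alone would not settle this; a scoring rule is needed too, and writing one down costs only wording.

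Much of this stands. Completed Cases is outcome-dependent, Section 18.2 is silent on both points, and the arithmetic is right. Three things limit it.

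- **No such choice has been made.** A completers set is common as a supportive analysis. The set described by the intent-to-treat principle is the natural one to decide, and the SAP is the usual place to say so and to give the rule for missing outcomes. Section 18.2 does not confine the analyst to dropping leavers or counting them as failures: Kaplan-Meier and multiple imputation also give an interval for a difference in proportions.
- **The large error needs a large, lasting imbalance or worse-healing leavers.** Sections 10.2 and 10.3 keep subjects in follow-up whatever treatment option is chosen, so stopping the dressing is not leaving. Treatment after Day 28 is at the investigator's discretion in both arms, so loss driven by the assigned dressing is most plausible early. That pattern gives 6.9%.
- **A decisive Kaplan-Meier estimate is a trade-off, not a correction.** If subjects with poorly healing wounds are the ones who leave, it errs more than counting leavers as not healed: 9% against 2%, or 20% against 5%.

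**Conclusion.** No change to the plan follows. Completed Cases would be a poor basis for the primary conclusion, but the protocol does not make it one. The unnamed deciding set and the missing scoring rule are gaps in detail that the protocol assigns to the SAP. An analyst following Section 18.7 would fill them sensibly: Full Analysis decides, Per Protocol supports, Completed Cases describes. Going further and prescribing one estimator would exchange one assumption about leavers for another.

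Under equal or modestly different loss (about 5% to 17% per arm), with leaving unrelated to later healing and one wound per subject, Completed Cases gives false non-inferiority of about 6% to 7% instead of 5%. The larger figures, from 9% to 37%, need a sustained threefold difference in leaving, leavers who would heal worse, or both. Every loss rate here is an assumption, because the documents state none. The conclusion also assumes that the SAP, which could not be checked, does not give Completed Cases the deciding role.

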19 CONFLICT OF INTEREST

The independence of this study from any actual or perceived influence, such as by the medical device industry, is critical. Therefore, any actual conflict of interest of a person who has a role in the design, conduct, analysis, publication, or any aspect of this trial will be disclosed and managed. Furthermore, persons who have a perceived conflict of interest will be required to have such conflicts managed in a way that is appropriate to their participation in the design and conduct of this trial. The Sponsor has established procedures for all Investigators to disclose all conflicts of interest and will establish a mechanism for the management of all reported dualities of interest.

20 GOOD CLINICAL PRACTICE AND STATEMENTS OF COMPLIANCE

20.1 Ethical Approval

The protocol will be reviewed by a properly constituted ethics committee. A copy of the written ethical approval will be sent to the Sponsor/designee.

Subject recruitment will not commence until appropriate ethical approvals/opinions have been received, and as appropriate, the applicable agreement(s) between the Sponsor and the Investigator have been documented. Any additional requirements imposed by the ethics committee will be incorporated into the protocol as required.

20.2 Protocol Modifications

Modifications to this protocol may be necessary. In collaboration with the Investigator(s), modification will be documented and submitted for ethical and regulatory approval (as required) prior to implementation. All changes will be evaluated for impact per Sponsor standard operating procedures (SOPs). Modifications will be considered implemented after all ethical and regulatory approvals (as required) are received and all key Sponsor and site staff have been trained.

20.3 Periodic Reviews

Ongoing review by IRB/EC is required for the duration of the clinical study. The Investigator will comply with local IRB/EC requirements for ongoing reviews.

20.4 Insurance

The Sponsor shall provide clinical study related insurance covering the reasonable, and necessary costs of diagnostic, therapeutic and medical treatment including hospitalization costs (treatment costs) for such participant injuries following the administration or use of the study device(s) in accordance with this clinical investigational plan and in accordance with the national regulations. The Sponsor may reimburse the institution and/or study participants for treatment costs, depending on who incurred such treatment costs if (i) the injury is attributable to the negligence or misconduct of any agent or employee of the institution or Investigator, or the failure of such persons to comply with a study protocol, (ii) the treatment costs are covered by the study participant's medical or hospital insurance coverage, or (iii) the treatment costs arose as a result of the treatment of normal progression of the study participant's disease or injuries resulting from interventions that the study participants would have incurred had they not participated in the study.

20.5 Patients' Compensation

Subjects may be compensated for their time and inconvenience. Details of any remuneration will be documented in the Patient/Participant Information Sheet.

20.6 Principal Investigator, Coordinating Investigator(S), Investigational Sites and External Organisations

The Name(s) and Address(es) of the sites at which this study is to be conducted is maintained as part of the Sponsor's files. The files will include the different roles, responsibilities, and qualifications of these investigators.

The Name(s) and Address(es) of the external organisation(s), such as core laboratories, CRO consultants, etc. which assist in this study are maintained as part of the Sponsor's files.

20.7 Public Registration and Publication

The Sponsor shall ensure that this study will comply with required national registration requirements. This study will be conducted in accordance with the applicable publication and data sharing policies and regulations. When applicable, attempts will be made to publish results. Publication rules will follow international recommendations.

22 GLOSSARY, ABBREVIATIONS & ACRONYMS

Abbreviation	Term
AE	Adverse Event
BMI	Body Mass Index
CRF	Case Report Form
CRO	Contract Research Organisation
EC	Ethics Committee
EU	European Union
FDA	Food and Drug Administration
GCP	Good Clinical Practice
IC	Informed Consent
ICH	International Conference for Harmonisation
IEC	Independent Ethics Committee
IFU	Instructions for Use
ITT	Intent to Treat
IRB	Institutional Review Board
MDR	Medical Device Regulations
PP	Per Protocol Population
QoL	Quality of Life
RCT	Randomised Control Trial
SAE	Serious Adverse Event
SAP	Statistical Analysis Plan
SOP	Standard Operating Procedure
TILI	Therapeutic Index for Local Infections score
UADE	Unanticipated Adverse Device Effect
VLU	Venus Leg Ulcer
